6.5. Planned Analyses

The following analyses have been or will be conducted on cleaned data and may be combined depending on study timelines.

1. An interim analysis of safety and immunogenicity data collected from Visit Day 1 through Day 84 (Month 3) was planned for Part 1. Due to the COVID-19 pandemic, this interim analysis was performed based on a subset of participants who had completed 3 months of safety and immunogenicity assessments as of 26 May 2020. This analysis served as the basis for selection of the mRNA-1647 dose level for implementation in Part 2 and in subsequent trials. Pre-identified Sponsor team members were unblinded to treatment group-level results. Participants, Investigators, and study sites remained blinded. Additional analyses of safety and immunogenicity data collected from Visit Day 1 through Day 84 (Month 3) could have been performed for all participants in Part 1 and for all participants in Part 2 after all participants in Part 2 had completed 3 months of assessments, and available safety or immunogenicity data up to Day 196 (Month 7) could

also have been summarized as part of these interim analyses. However, these additional 3-month interim analyses were deemed unnecessary by the Sponsor and hence were not performed.

2. A Part 1 7-month interim analysis of safety and immunogenicity data collected from Visit Day 1 through Day 196 (Month 7) was performed after all Part 1 participants had completed 7 months of safety and immunogenicity assessments (data cutoff date 16 Sep 2020). Pre-identified Sponsor team members were unblinded to both treatment group-level results and individual listings. Study participants, Investigators, and study sites remained blinded.
3. A Part 2 7-month interim analysis of safety and immunogenicity data collected from Visit Day 1 through Day 196 (Month 7) was performed after all Part 2 participants had completed 7 months of safety and immunogenicity assessments (data cutoff date 18 Feb 2022). Available safety and immunogenicity data from Visit Day 1 through the end of the trial for all Part 1 participants were also summarized as part of this interim analysis. Pre-identified Sponsor team members were unblinded to both treatment group-level results and individual listings. Study participants, Investigators, and study sites remained blinded until the completion of each individual participant's final study procedures, including final assessment and recording of MAAEs and SAEs, at which point the individual participant's treatment assignment may be unblinded using the IRT system to the Investigator, participant, Sponsor, and Sponsor representatives/delegates, as outlined in protocol Section 8.11 "Unblinding".
4. The final unblinded analysis of safety and immunogenicity data collected from Visit Day 1 through the end of the trial for all participants will be conducted when the database is cleaned and locked. Results of this analysis will be presented in a Clinical Study Report (CSR), including individual listings.

At an interim analysis when data from both Part 1 and Part 2 were available and in scope for the analysis, or at the final analysis when all participants in Part 1 and Part 2 have completed or discontinued from the study, data were/will be summarized and analyzed with Part 1 and Part 2 combined, unless otherwise specified.

7. Changes from Planned Analyses in Protocol

For the planned 7-month IAs, protocol Section 9.7 states "Available safety or immunogenicity data up to Day 336 (Month 12) may also be summarized as part of these interim analyses." However, at the time of planning the Part 2 7-month IA with the latest

data cutoff date of 18 Feb 2022 for Part 2 participants, all Part 1 participants either discontinued or completed the study up to the final visit at Month 18 for participants completing all 3 vaccinations. Therefore, the Part 2 7-month IA instead included all available safety and immunogenicity data from Visit Day 1 through the end of the trial for all Part 1 participants to make this analysis more comprehensive. This change did not impact the primary and/or key secondary objectives/hypotheses or the related statistical methods.

For the final analysis, the ELISpot assay planned in protocol Section 3.2.3 for the exploratory CMI endpoints was updated to an intracellular cytokine staining (ICS) assay internally qualified at Moderna Clinical Biomarker Lab (CBL) to measure a larger set of T-cell responses including the planned IFN- γ . The ICS assay was chosen since it can provide information about multiple T-cell responses utilizing the same number of PBMCs with higher sensitivity. The clinical protocol was not amended for this change in the CMI assay which was deemed to have no impact on the primary and/or key secondary objectives/hypotheses or the related statistical methods.

8. References

Department of Health and Human Services (DHHS), Food and Drug Administration, Center for Biologics Evaluation and Research (US). Guidance for industry: Toxicity grading scale for healthy adult and adolescent volunteers enrolled in preventive vaccine clinical trials. September 2007 [cited 2017 Jul 27] [10 screens]. Available from: <http://www.fda.gov/downloads/BiologicsBloodVaccines/GuidanceComplianceRegulatoryInformation/Guidances/Vaccines/ucm091977.pdf>.

9. List of Appendices

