### **5.2. Inclusion Criteria**

Participants are eligible to be included in the study only if all of the following criteria apply:

1. Age and sex
  - Part 1: Male or female 18-40 years of age at time of consent.
  - Part 2: Female 18-40 years of age at time of consent.
2. Understands and agrees to comply with the trial procedures and provides written informed consent.
3. According to the assessment of the Investigator, is in good general health and is capable of complying with trial procedures.
4. Body mass index (BMI) 18-35 kg/m^2.
5. Female participants of nonchildbearing potential may be enrolled in the study. Nonchildbearing potential is defined as surgically sterile (history of bilateral tubal ligation, bilateral oophorectomy, hysterectomy) or postmenopausal (defined as amenorrhea for  $\geq 12$  consecutive months prior to Screening without an alternative medical cause). A follicle-

stimulating hormone (FSH) level may be measured at the discretion of the Investigator to confirm postmenopausal status.

6. Female participants of childbearing potential may be enrolled in the study if the participant:
  - 1) has a negative pregnancy test at Screening and on the day of the first vaccination, and
  - 2) has practiced adequate contraception or has abstained from all activities that could result in pregnancy for at least 28 days prior to the first vaccination, and 3) has agreed to continue adequate contraception through 3 months following the last vaccination, and 4) is not currently breastfeeding.

Adequate female contraception is defined as consistent and correct use of a US Food and Drug Administration (FDA) approved contraceptive method in accordance with the product label. For example:

- Barrier method (such as condoms, diaphragm, or cervical cap) used in conjunction with spermicide
- Intrauterine device
- Prescription hormonal contraceptive taken or administered via oral (pill), transdermal (patch), subdermal, or IM route
- Sterilization of a female participant's monogamous male partner prior to entry into the study

Note: periodic abstinence (eg, calendar, ovulation, symptothermal, post-ovulation methods) and withdrawal are not acceptable methods of contraception.

7. Male participants engaging in activity that could result in pregnancy of sexual partners must agree to practice adequate contraception from the time of the first vaccination and through 3 months after the last vaccination.

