7. Has received or plans to receive a vaccine  $\leq 28$  days prior to the first vaccination or plans to receive a non-study vaccine within 28 days prior to or after any study vaccination, except for any licensed influenza vaccine which can be administered  $>14$  days before or after any study vaccination. COVID-19 vaccines (regardless of manufacturer) may be administered  $> 7$  days but preferably  $> 14$  days before or after any study vaccination, with the intention of prioritizing COVID-19 vaccination over all other considerations.
8. Received systemic immunosuppressants or immune-modifying drugs for  $> 14$  days in total within 6 months prior to the day of enrollment (for corticosteroids,  $\geq 20$  mg/day of prednisone equivalent). Topical tacrolimus is allowed if not used within 14 days prior to the day of enrollment. Inhaled, nasal, and topical steroids are allowed.

9. Receipt of intravenous immunoglobulins or plasma products within 3 months prior to the day of the first study vaccination.
10. Part 1 participants only: Previous receipt of medications in LNP formulation.
11. Has donated  $\geq 450$  mL of blood products within 28 days of the Screening visit. Participants engaging in blood sampling for cell-mediated immunogenicity should be advised to refrain from blood donation through the vaccination period (Day 1 through Month 7).
12. Participated in an interventional clinical trial within 28 days prior to the day of enrollment or plans to do so while enrolled in this trial.
13. Is an immediate family member or household member of trial personnel.

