- For laboratory assessments, if majority of results are indefinite, imputation of these values will be considered. If the laboratory results are reported as below the LLOQ (eg, < 0.1), the numeric values will be imputed by $0.5 \times \text{LLOQ}$ in the summary. If the laboratory results are reported as greater than the ULOQ (eg, > 3000), the numeric values will be imputed by ULOQ in the summary.

Other incomplete/missing data will not be imputed, unless specified otherwise.

The following **vaccination groups** will be used for summary purposes:

- mRNA-1647 vaccine: **CCI**

- mRNA-1647 vaccine: CCI
- mRNA-1647 vaccine: CCI
- mRNA-1647 vaccine: Total
- Placebo

Summary by study part and CMV serostatus:

All analyses and data summaries/displays will be provided by CMV serostatus (CMV-seropositive and CMV-seronegative) unless otherwise specified. Analyses and data summaries/displays may be provided by study part (Part 1, Part 2, and/or overall) when specified, please also refer to [Section 6.5 Planned Analyses](#).

For those subjects who were CMV seronegative at Screening and became CMV seropositive at Baseline (before or on the day of 1st vaccination), the subjects will be:

- included in the Randomized Set under the CMV status group the subjects were randomized under, ie, CMV seronegative
- included in the Solicited Safety Set and Safety Set, under CMV seropositive group
- included in the FAS, under CMV seropositive group
- excluded from the PP Set for Antibody-Mediated Immunogenicity data and CMI data

All analyses will be conducted using SAS Version 9.4 or higher.

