- In the CMV-seropositive groups, proportion of subjects who achieve serum anti-CMV neutralizing antibody titers against epithelial cell infection and anti-CMV antibody titers against fibroblast infection greater than the third quartile of the serum anti-CMV antibody titers overall distribution at baseline (Day 1) will be tabulated.
- Anti-CMV neutralizing antibody titers against epithelial cell infection and anti-CMV neutralizing antibody titers against fibroblast infection will be displayed using reverse cumulative curves.
- For serum anti-CMV neutralizing antibody titers against epithelial cell infection and anti-CMV neutralizing antibody titers against fibroblast infection respectively, the GMT at Month 3, Month 7, Month 12, and Month 18 for each vaccination group, and

the ratio of GMT of mRNA-1647 **CCI**, mRNA-1647 **CCI**, and mRNA-1647 **CCI** vs. Placebo respectively, will be estimated based on an analysis of covariance (ANCOVA) model that will be carried out for CMV-seropositive groups and CMV-seronegative groups separately using the PP Set. For Month 3, the dependent variable will be the nAb at Month 3 with the vaccination group as a factor and the baseline values as covariate (if applicable, ie, for CMV-seropositive groups only). The GMT and corresponding 95% CI for each vaccination group, and the ratio of GMT of mRNA-1647 **CCI**, mRNA-1647 **CCI**, and mRNA-1647 **CCI** vs. Placebo respectively, together with corresponding 95% CI will be provided. A similar model at Month 7, Month 12, and Month 18 will be carried out for those who were CMV-seronegative groups, and CMV-seropositive groups separately using the PP set.

Similar analyses will be performed for gB-binding antibodies and Pentamer-binding antibodies as measured by ELISA.

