6.4.4. Sensitivity/Supportive Analysis

In the final analysis of antibody-mediated immunogenicity endpoints, the following sensitivity analyses may be performed to assess the impact of widened visit window and missing data due to COVID-19 pandemic.

1. In Part 1, protocol amendment 2 widened the visit window in response to the COVID-19 pandemic. A sensitivity analysis may be carried out to assess the impact on the widened visit windows on immunogenicity endpoints. In this sensitivity analysis, immunogenicity data which complied with the vaccination and/or immunogenicity assessment schedules under protocol amendment 2, but which did not comply with the schedules under protocol amendment 1, the last version of protocol before the protocol amendment 2, will be excluded from this sensitivity analysis.
2. A restricted maximum likelihood (REML)-based mixed-effect model for repeated measures (MMRM), a model-based missing data approach, will be used for the log-

transformed titer based on the PP set. MMRM is based on the assumption of missing at random.

The analysis will be carried out using SAS PROC MIXED and conducted for CMV-seropositive groups and CMV-seronegative groups separately. The model will include all available log-transformed anti-body titers at each post-baseline visit as the dependent variable, vaccination groups, visit (as a class variable), baseline values (if applicable, ie, for CMV-seropositive groups only), and interaction of vaccination group and visit as fixed effects, and subject as a random effect. An unstructured covariance structure will be used to model the within-subject errors. If the model fails to converge, a compound symmetry covariance structure will be considered. The degrees of freedom of the denominator will be approximated by the Kenward-Roger method. The geometric least squares mean (GLSM) and corresponding 2-sided 95% CI for the anti-body titers for each vaccination group will be provided by visit. In addition, the ratio of GLSM and the corresponding 2-sided 95% CI will be provided to assess the treatment difference between each of mRNA-1647 group **CCI** vs. the Placebo group at each visit. The GLSM, difference in GLSM, and corresponding 95% CI results in log-transformed scale estimated from the model will be back-transformed to obtain these estimates in the original scale.

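### The final analysis pools Part 1 and Part 2 with no committed by-part display, so any difference between the parts enters the dose comparisons and the unselected-dose-versus-placebo ratios

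*SAP*

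**What the plan says.** SAP 6.5 sets the rule for the final analysis, and for any interim with both parts in scope: "data were/will be summarized and analyzed with Part 1 and Part 2 combined, unless otherwise specified". SAP 6.1 defines one set of vaccination groups: three dose levels, their total, and a single placebo group. It says that displays "may be provided by study part (Part 1, Part 2, and/or overall) when specified", but no section of the SAP specifies one for the final analysis.

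The models follow the same structure. In the ANCOVA of SAP 6.4.2, "the dependent variable will be the nAb at Month 3 with the vaccination group as a factor and the baseline values as covariate"; the covariate applies to seropositive participants only, and Months 7, 12 and 18 are treated alike. The MMRM of SAP 6.4.4 has vaccination group, "visit (as a class variable), baseline values (if applicable, ie, for CMV-seropositive groups only), and interaction of vaccination group and visit as fixed effects". Both are fitted separately by serostatus, both compare each dose with placebo, and neither has a term for part or sex. The sensitivity analyses address widened visit windows and missing data.

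The parts differ by design. Protocol 5.2 has "Part 1: Male or female 18-40 years of age at time of consent" against "Part 2: Female 18-40 years of age at time of consent". Protocol 5.3 lists this exclusion: "Part 1 participants only: Previous receipt of medications in LNP formulation". Part 2 was added by Amendment 3 (04 September 2020) and uses only the selected dose and placebo. Its screening window for seropositive participants is 42 days rather than 28 (Protocol 4.1.1), and multiple-dose vial preparation is allowed (Protocol 6.2.2).

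**The concern.** The primary objectives concern safety and neutralizing antibody at different dose levels, so readers of the final report will compare the dose columns. In the pooled tables those columns hold different populations. The selected dose is mostly Part 2, the placebo group is partly Part 2, and the other two doses are entirely Part 1. If sex, calendar period, previous LNP exposure or preparation affects titers or reactogenicity, the effect appears as a difference between doses. It also enters a ratio that the SAP does plan: each unselected dose against a placebo group drawn partly from a part in which that dose was never given. At stake are the estimates and intervals in the clinical study report. Nothing is tested, so no error rate is involved.

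**Working it through.** **Inputs.** Arm sizes and the 3:1 ratio come from Protocol 4.1. Part 1 has 60 seronegative and 24 seropositive participants per dose level; Part 2 has 80 and 120.

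**The plan's own figures.** Part 1 vaccine: 252 × 0.75 = 189. Part 2 vaccine: 200 × 0.75 = 150. 1 − 0.98^189 = 97.8% (stated as above 95%) and 1 − 0.98^150 = 95.2% (stated as above 90%). Totals are 189 + 150 = 339 vaccine and 63 + 50 = 113 placebo, as in Protocol 2.3. All reproduce.

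**Part 2 share of each pooled column.**

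| Group | Seronegative | Seropositive |
|---|---|---|
| Selected dose | 60/(45+60) = 57.1% | 90/(18+90) = 83.3% |
| Placebo | 20/(45+20) = 30.8% | 30/(18+30) = 62.5% |
| Each other dose | 0/45 = 0% | 0/18 = 0% |
| Total vaccine | 60/195 = 30.8% | 90/144 = 62.5% |

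At the 502-participant maximum the shares are 62.5% and 86.2% for the selected dose, and 35.7% and 67.6% for placebo.

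**Effect on the ratios.** The documents give no part effect. Assume that Part 2 titers are d times Part 1 titers for reasons other than dose, with d from 1.2 to 1.5, in vaccine and placebo alike. An unadjusted ratio is then multiplied by d^(difference in Part 2 share).

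| Contrast | Seronegative: exponent, factor | Seropositive: exponent, factor |
|---|---|---|
| Selected vs placebo (planned) | 0.264, 1.05 to 1.11 | 0.208, 1.04 to 1.09 |
| Unselected vs placebo (planned) | −0.308, 0.95 to 0.88 | −0.625, 0.89 to 0.78 |
| Selected vs unselected (read across columns) | 0.571, 1.11 to 1.26 | 0.833, 1.16 to 1.40 |
| Total vaccine vs placebo | 0, 1.00 | 0, 1.00 |

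In the seropositive models the baseline covariate removes any part effect that acts through baseline titer, so that column is an upper guide. With d = 1 every factor is 1.

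**If part affects vaccine response only.** Placebo does not move and pooling leaves unselected versus placebo unbiased. Selected versus unselected keeps the factors above. Selected versus placebo becomes a blend of two part-specific ratios, d^0.571 or d^0.833 above its Part 1 value.

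**Would a part term in the model cure it?** If part acts additively on all groups, yes. The standard error rises by 3.5% and 2.7% (seronegative, seropositive) for selected versus placebo, 3.1% and 9.3% for unselected versus placebo, and 12.2% and 18.7% for selected versus unselected.

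If part affects vaccinees only, the common part term is a weighted average with weights n1·n2/(n1+n2).
- Seronegative: 45·60/105 = 25.7 from vaccine and 45·20/65 = 13.8 from placebo, so it estimates 25.7/39.6 = 0.65 log d. Unselected versus placebo, unbiased before, gains d^(0.308 × 0.65) = d^0.20, or 1.04 to 1.08. Selected versus unselected keeps d^(0.571 × 0.35) = d^0.20.
- Seropositive: 18·90/108 = 15 and 18·30/48 = 11.25, giving 0.571 log d. Unselected versus placebo gains d^(0.625 × 0.571) = d^0.36, or 1.07 to 1.16.

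**Precision if restricted to Part 1** (in units of a common residual SD).
- Unselected versus placebo, seronegative: √(1/45+1/45) = 0.211 against √(1/45+1/65) = 0.194, 9% wider. Seropositive: 0.333 against 0.276, 21% wider.
- Selected versus unselected, seronegative: 0.211 against 0.178, 18% wider. Seropositive: 0.333 against 0.255, 31% wider.

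**The case against.** The case for leaving the plan alone has several good points.

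- **No dose-to-dose ratio is planned.** The models compare each dose with placebo only. A reader might infer that the SAP itself estimates a dose contrast biased by up to 1.40; it does not. That figure describes a comparison made by eye across columns. This stands, but the tables invite the comparison and the objectives ask for it.
- **A part-free dose comparison already exists.** The dose was chosen on Part 1 data (cutoff 26 May 2020), and a Part 1 interim covered all Part 1 participants through Month 7 (cutoff 16 September 2020). A reader might infer that pooling undermines dose selection; the documents rule that out. What remains open is Months 12 and 18, and the lack of any commitment to by-part results in the final report.
- **GMR and fold-rise are within-subject.** Stable differences in titer level cancel in them. Differences in vaccine response do not.
- **By-part tables may be in the shells.** The SAP relies on table shells that are not part of these documents. They may contain such tables, but the SAP does not commit to them.
- **Part 1 is not fully concurrent either.** Doses were enrolled sequentially and their three placebo cohorts are merged. This stands: restricting to Part 1 removes confounding by part only.
- **Overlap with COVID-19 vaccination.** A reader might treat this as peculiar to Part 2. Part 1 follow-up also runs to Day 504, and COVID-19 vaccination is recorded throughout, so the documents do not support that.

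**Conclusion.** The concern holds as a gap in presentation and interpretation that should be closed before the final lock. Pooling is the default, no by-part display is committed to, and the imbalance in part is fixed by design. It matters most for side-by-side readings of the doses and for the planned ratios of the unselected doses to placebo. Selected dose versus placebo is affected less (share gaps of 26 and 21 points) when part shifts vaccine and placebo alike, and total vaccine versus placebo is balanced by part.

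The size is unknown. Every factor above rests on an assumed part effect, and the bias is zero if there is none.

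Two stronger readings are tempting. One is that the selected dose is wholly confounded with Part 2. It is not: the selected dose and placebo occur in both parts, and Part 1 also enrolls women. The other is that the main models must carry part and sex terms. The documents do not support that as the primary remedy, because an additive term can bias the unselected-dose-versus-placebo ratio when part changes vaccine response but not placebo titers. That is plausible in seronegative participants, whose placebo titers are likely to lie near the assay floor.

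**What to change.** In SAP 6.5, before the final database lock:

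1. Commit to showing GMT, GMR, fold-rise, solicited reactions and unsolicited adverse events for Part 1 alone and Part 2 alone beside the combined column, by serostatus.
2. State that between-dose comparisons and unselected-dose-versus-placebo ratios, including those at Months 12 and 18, rest on Part 1 data.
3. Optionally, in SAP 6.4.4, add an ANCOVA and MMRM adjusted for part and sex as a sensitivity analysis only, noting that an additive part term may mis-adjust.
4. State as a limitation that Part 1 doses were enrolled sequentially, so Part 1 comparisons are free of confounding by part but not of all non-concurrency.

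No new data are needed. The cost is SAP wording, extra table columns, and wider intervals for the contrasts restricted to Part 1: about 9% and 21% (seronegative, seropositive) for unselected dose versus placebo, and 18% and 31% for selected versus unselected dose. The combined column and the planned total-vaccine summaries can stay as they are.
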